**Methods.** Patients who are surgical candidates for a one-level anterior/posterior lumbar fusion will be randomized to IBG or one of 4 types of bone graft alternatives (small Medtronic Infuse BMP, Orthofix Trinity allograft bone marrow derived stem cells combined with morcelized cancellous allograft, Allosource Allostem fat derived stem cells combined with morcelized cancellous allograft, or Nutech Nucel amnion derived stem cells combined with morcelized cancellous allograft). There will be 20 patients in each group. All anterior fusions will use BMP; the study only applies to the posterior fusion. Neither patient nor surgeon is blinded to the posterior type of bone graft. The volume of bone graft is the same for each type, approximately 5cc. The decortication part of the fusion is identical for all patients, as is the type of instrumentation (anterior plate and posterior facet screws). Limited CT scans of the fusion will be obtained at approximately one year postoperatively to assess fusion success of both anterior and posterior regions. The limited CT scan results in approximately 2.88 mSv radiation exposure, or similar to one year's worth of background radiation. Secondary endpoints are patient outcomes for pain and function using standard VAS pain scales and Oswestry Disability Index at one year postoperatively will be assessed to ascertain the relationship between clinical success and fusion success since prior studies suggest that success is only related to the status of anterior fusion.

**4 Study Design/Protocol** (Please answer the questions below and attach the study protocol):

- a. What are the objectives of the proposed research/project?

*Evaluate the effectiveness of 5 types of bone graft material in obtaining a solid posterior fusion for one level anterior/posterior lumbar spinal fusion.*

- b. What is the significance of the proposed study? (Provide the context for the study, and the rationale. What is known about the topic? Why is the study important? What kind of answers will the study provide?)

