*Iliac bone autograft is an additional procedure with known morbidity and high rate of residual pain postoperatively at the graft donor site leading to reduced outcomes. Bone morphogenic protein is effective in obtaining fusion but is used off label, has multiple side effects, and is expensive to hospital systems. Stem cell bone products are an attractive alternative that avoids pain related to the graft donor site and have a far better safety profile than BMP.*

- What will subjects be asked to do?

*Patients who are scheduled to undergo a single level lumbar anterior/posterior spinal fusion with instrumentation will be eligible to participate. Subjects will be asked to agree to be randomized to one of five types of bone graft for the posterior portion of their fusion surgery.*

- What is the study design?

*Prospective, non-blinded, randomized study design of 5 types of bone graft material applied to 100 patients (20 patients per group).*

- c. Describe the proposed data collection procedures. Attach any forms such as surveys, chart abstraction or other data collection forms.

*Data collection includes age, date of surgery, date of follow-up CT scan (>9 months postop), assessment of fusion at follow-up, smoking and osteoporosis status (which may affect fusion status), type of bone graft used for the anterior procedure (all will be bone morphogenic protein combined with local autograft), type of bone graft used for the posterior procedure.*

- d. List the routine medical related costs for this research/project/trial.

- 1) **ROUTINE OR STANDARD MEDICAL CARE:** This includes items or services that are typically provided absent a clinical trial and those required for the provision of the investigational item or service, as well as appropriate monitoring, prevention of complications, and the diagnosis or treatment of complications arising from the provision of an investigational item or service.

*The fusion surgery is considered standard of care. The costs of a single level lumbar fusion is information known to HealthEast as they are the entity that charges for this type of surgery. The charges and reimbursement for spinal surgery at HealthEast has not been shared with the investigator.*

- 2) **STUDY RELATED CARE:** List the additional items or services required for the provision of the investigational item or service

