*Additional items related to cost are limited CT scan at >9months postoperatively. This cost is \$265 per patient and will be paid for by the principal investigator/Midwest Spine & Brain Institute.*

3) **STUDY SPECIFIC CARE:** List items or services furnished solely to satisfy data collection, analysis needs, or to determine trial eligibility.

*Data will be collected by the PI on a personal password protected laptop computer. Statistical analysis will be obtained from a third party.*

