## 5 Financial Information

- a. Will this project be funded by, or supported by a center or cooperative group(s) that is funded by NIH, CDC, AHRQ, HCFA, or the VA?  
 NO       YES - Specify:
- b. Will this project be funded through *other* outside granting agencies?  
If yes, please list.  
 NO       YES - Source(s):
- c. Do any of the investigators have a financial interest with the funding source/study sponsor, and if so, what type (e.g. shareholder, stock options, paid consultant or medical director, travel expense reimbursement, provision of office supplies or equipment)?  
 NO       YES - What Type?
- d. Does this study have an IND number?  
 NO       YES - Number:
- e. Does this study have an IDE number?  
 NO       YES - Number:
- f. Is this trial exempt from having an IND under 21 CFR 312.2(b)(1)?  
 NO       YES       NA
- g. Inclusive Date of Project:  
Start Date: October 1, 2015 End Date: January 1, 2020
- h. Aspects of this study involving the use of human subjects will be conducted in:  
 Hospital     Physician's Office/Clinic     Other (please identify):

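### Does the fusion CT, with a one-year target and a nine-month floor but no stated upper limit, leave the main outcome without a time point?

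*Protocol*

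**What the plan says.** The protocol mentions the timing of the fusion CT in three places.

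- **Section 3, Abstract, Methods:** "Limited CT scans of the fusion will be obtained at approximately one year postoperatively to assess fusion success of both anterior and posterior regions". The same paragraph sets the clinical outcomes: "Secondary endpoints are patient outcomes for pain and function using standard VAS pain scales and Oswestry Disability Index at one year postoperatively". They are to be related to fusion status.
- **Section 4, item c (data collection):** the list of data fields includes "date of follow-up CT scan (>9 months postop), assessment of fusion at follow-up". Date of surgery is in the same list.
- **Section 4d(2) (study-related care):** "Additional items related to cost are limited CT scan at >9months postoperatively", with a fixed cost per patient paid by the investigator's side.

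The objective in section 4, item a, is to "Evaluate the effectiveness of 5 types of bone graft material in obtaining a solid posterior fusion", and the CT supplies that outcome. The only other time limit is the project period in section 5, item g: "Start Date: October 1, 2015 End Date: January 1, 2020". No section gives a latest acceptable scan date or a tolerance around one year.

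**The concern.** Fusion develops over time, so a scan at 9 months and one at 18 months do not measure the same thing, and a mistimed scan cannot be repeated at the right time. Two of the three statements give only a lower limit. If they govern, the outcome could mix very different healing times.

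Two consequences would follow. First, "Neither patient nor surgeon is blinded to the posterior type of bone graft", so scan dates could drift with graft type or symptoms, and a timing difference between arms could pass for a graft effect. Second, the pain and disability scores are fixed at one year and are to be set against fusion status. A CT taken months away would pair a one-year score with fusion at another time, in any arm.

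**Working it through.** **1. The passages side by side.**

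| Place | Purpose of the text | Timing |
|---|---|---|
| Abstract, Methods | how the study is performed | about 12 months |
| Section 4, item c | list of data fields | more than 9 months |
| Section 4d(2) | cost item | more than 9 months |
| Abstract, Methods (VAS, ODI) | secondary endpoints | one year |

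A scan at about 12 months satisfies every row. The Methods sentence says when scans will be done; the other two CT entries describe a data field and a cost. The natural reading is a target of one year and nothing earlier than nine months. There is no contradiction.

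**2. The widest literal range.** 1 October 2015 to 1 January 2020 is 1,553 days; 1,553 / 30.4375 = 51.0 months. The range of 9 to 51 months therefore needs a patient operated on at the start, scanned at the very end, with the one-year target ignored. A 51-month scan is not approximately one year.

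**3. What imperfect timing could do.** The protocol gives no fusion rate or curve, so these are assumptions:

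- Exponential: F(t) = 1 − exp(−λt), λ = −ln(1 − F12)/12, with F12 (the proportion fused at 12 months) = 0.60, 0.80 or 0.90.
- Plateau: F(t) = 0.85 × (1 − exp(−λt)), λ = −ln(1 − 0.80/0.85)/12, so F12 = 0.80.

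Differences in percentage points:

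| Curve | F12 − F9 | F18 − F12 | F13 − F11 |
|---|---|---|---|
| Exponential, 60% | 10.3 | 14.7 | 6.1 |
| Exponential, 80% | 9.9 | 11.1 | 5.4 |
| Exponential, 90% | 7.8 | 6.8 | 3.9 |
| Plateau, 80% | 5.2 | 3.8 | 2.4 |

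The first two columns apply to patients scanned at 9 or 18 months. The last is the shift if one arm averaged 11 months and another 13.

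**4. How large a chance gap between arms would be.** With 20 per arm, the standard error of the difference in mean scan time is SD × √(2/20). For an assumed SD of 2 months it is 0.63 months; for 3 months it is 0.95. A 2-month gap is then 2/0.63 = 3.2 or 2/0.95 = 2.1 standard errors. A one-standard-error gap centred at 12 months shifts the difference in fusion rates as follows:

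| Curve | SD 2 months | SD 3 months |
|---|---|---|
| Exponential, 60% | 1.9 | 2.9 |
| Exponential, 80% | 1.7 | 2.5 |
| Exponential, 90% | 1.2 | 1.8 |
| Plateau, 80% | 0.7 | 1.1 |

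**5. Against sampling error.** The standard error of a difference between two arms of 20 is √(2p(1 − p)/20):

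- p = 0.60: √(0.48/20) = 15.5 points
- p = 0.80: √(0.32/20) = 12.6 points
- p = 0.90: √(0.18/20) = 9.5 points

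Matching each curve to its own standard error, the largest ratio is 2.5/12.6, about 0.2. A typical chance imbalance in timing is at most about a fifth of the sampling error already present.

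**The case for a change.** The best case for a change is that scan timing is a matter of conduct. An analysis plan can restrict or adjust for scan dates, but it cannot move a scan already taken. A two-sided window would cost one sentence. The link between fusion and one-year pain and disability is also blurred by off-time scans without any bias between arms. In an extreme case, with identical grafts but one whole arm scanned at 9 months and another at 18, the exponential curves with 60–90% fused at 12 months give a spurious difference of 15 to 25 points. The chance of p < 0.05 with 20 per arm is then about 32–39%.

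Part of this stands: no upper limit is written, and a stated tolerance would be tidier. But the extreme case needs whole arms to depart from the written target in opposite directions, and nothing in the protocol points that way. The CT is listed as study-related care at a set cost per patient, which suggests a planned scan for everyone and not one prompted by symptoms. The timing text does not vary by arm, and scan-time variation common to all arms does not bias the graft comparison. The exponential curves also assume that everyone eventually fuses; the plateau curve gives the smallest shift on every measure. For the fusion–outcome relation, CT and scores already share a one-year target, so mismatch arises only for scans that miss it.

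**Conclusion.** No change follows. The CT has a stated time point of about one year, aligned with VAS and ODI, and a compatible nine-month floor. The gap is an unstated upper tolerance, which staff following the whole document would fill sensibly by scanning every arm at about one year. Because surgery and CT dates are both collected, each patient's interval is known, and a sensitivity analysis by scan time needs nothing new. Such an analysis, like the handling of late scans, is commonly left to the statistical analysis plan, which is not at hand.

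The likely effect on the graft comparison is small: about 0.7–2.9 points for a one-standard-error chance imbalance, against a sampling standard error of about 9.5–15.5 points. These figures rest on assumed fusion curves and an assumed scan-time SD of 2–3 months. They also assume that scan dates do not depend on graft; the protocol gives no evidence that they would, though the open-label design cannot rule it out. The reading of the text as a target plus a floor does not depend on these assumptions.

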## 5 Financial Information

- a. Will this project be funded by, or supported by a center or cooperative group(s) that is funded by NIH, CDC, AHRQ, HCFA, or the VA?  
 NO       YES - Specify:
- b. Will this project be funded through *other* outside granting agencies?  
If yes, please list.  
 NO       YES - Source(s):
- c. Do any of the investigators have a financial interest with the funding source/study sponsor, and if so, what type (e.g. shareholder, stock options, paid consultant or medical director, travel expense reimbursement, provision of office supplies or equipment)?  
 NO       YES - What Type?
- d. Does this study have an IND number?  
 NO       YES - Number:
- e. Does this study have an IDE number?  
 NO       YES - Number:
- f. Is this trial exempt from having an IND under 21 CFR 312.2(b)(1)?  
 NO       YES       NA
- g. Inclusive Date of Project:  
Start Date: October 1, 2015 End Date: January 1, 2020
- h. Aspects of this study involving the use of human subjects will be conducted in:  
 Hospital     Physician's Office/Clinic     Other (please identify):

## 6 Subject Population

- a. Check all that apply:  
 Inpatient     Outpatient     Healthy Volunteers     Other
- b. Describe criteria for inclusion and exclusion of subjects in this study:
  - Inclusion Criteria:  
*Lumbar spinal fusion of a single segment for a degenerative condition; age 18 – 65*
  - Exclusion Criteria:  
*Prior lumbar fusion surgery; prior abdominal surgery precluding access to the anterior spine; lytic spondylolisthesis; high grade stenosis requiring partial or complete facetectomy*
- c. If the study includes use of clinical patients, will approval be obtained from the attending M.D.?  
 NO       YES - Describe how:

*Consent will be obtained at the time of preoperative discussion in patients who desire to proceed with fusion surgery after having failed non-operative treatment for their degenerative condition. Risk and benefits of surgery as well as specific risks related to bone graft products will be presented.*

d. How many subjects do you plan to enroll?

100

e. Please indicate the approximate number of subjects to be enrolled for each gender category:

40 Male      60 Female

f. Expected Age Range-please check all that apply:

0-7 (include parental consent form)  
 8-17 (include parental consent form and child assent form)  
 18-65  
 65 and older

Exact ages to be included:18-65

g. Protected Populations to be Studied-please check all that apply

Pregnant women  
 Embryos/Fetuses  
 Prisoners  
 Minors (under age 18)  
 Mentally/Emotionally/Developmentally Disabled Persons  
 NA

h. If this is a multi-center study, what is the total number of subjects to be enrolled from all centers:

NA

i. How will subjects be chosen? (e.g. records, classes, referral)

*Patients who are followed and treated for their spinal condition and who meet the entry criteria will be enrolled from the PI's clinical practice.*

j. Will subjects receive any inducements or rewards for participating in the study?

NO       YES - Please explain:

k. Will subjects be charged for any research-related procedures?

NO       YES - If amount is known, please list:

## 7 Risk

The purpose of this section is to determine whether the human subjects involved in the proposed research project will be placed at risk. In order to help determine what risk subjects will be exposed to, please answer the following questions:

DOES THE RESEARCH PLAN IN THIS PROJECT INVOLVE:	YES	NO
a. Possible invasion of privacy of subject or family, including use of personal information or records? .....		
b. The administration of physical stimuli other than auditory and visual stimuli associated with normal classroom situation? .....		
c. Deprivation of physiological requirements such as nutrition or sleep; manipulation of psychological and/or social variables (e.g. sensory deprivation, social isolation, psychological stresses, etc.)? .....		
d. Any probing for information in survey or interview that an individual might consider to be personal or sensitive? .....		
e. The requirement of physical exertion beyond normal classroom situations? .....		
f. The presentation to the subject of any materials which they might find to be offensive, threatening or degrading? .....		
g. Deception as part of the experimental procedure? If the study involves the use of deception, the protocol must include a description of this fact and the "debriefing procedure" which will be used upon completion of the study. .....		
h. The use of drugs? If yes, please comment on the preparation, dosage, toxicity, significant side effects, etc. .....		
i. Any surgical processes? .....		
j. Administration of approved/unapproved devices? .....		
k. Blood drawing, marrow biopsy sampling, biopsy of other tissues, etc (if "yes", state the amount (volume measure) and frequency at which samples are taken. The consent form must include lay term equivalents for the amount, e.g. teaspoons. Please distinguish between procedures that are diagnostic from procedures performed solely for research .....		
l. The use of radioisotopes, or other sources of ionizing radiation including X-rays? .....		
m. Use of controlled substances? .....		
n. Describe the nature and degree of risk or harm checked above:		

*The risks associated with obtaining iliac bone autograft and include pain, infection (<5%), pelvic fracture (very rare).*

*The limited post-procedure CT scan results in approximately 2.88mSv of radiation exposure, which is equivalent to one year's worth of background radiation.*

o. List any anticipated direct and/or societal benefits to participating in this research project. If none, state that fact here and in the consent form:

*The benefits are for future spinal fusion patients who may be able to avoid the morbidity related to harvesting iliac bone autograft yet still reliably obtain a solid posterior fusion using one of the alternative bone graft products evaluated in this study.*

p. Do the benefits of this study outweigh the risks? ..... Yes  No

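### Does the risk item (7n) need to change because it describes only iliac-harvest and CT risks?

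*Protocol*

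**What the plan says.** Section 7 of the protocol (an application for research and ethics review) is a tick list followed by free text. Item 7i, "Any surgical processes", is ticked Yes, as are privacy (7a) and ionizing radiation (7l). Drugs (7h) and devices (7j) are ticked No. Item 7n then asks the applicant to "Describe the nature and degree of risk or harm checked above". The reply has two entries: "The risks associated with obtaining iliac bone autograft and include pain, infection (<5%), pelvic fracture (very rare", and the follow-up CT at about 2.88 mSv.

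Other sections say more about the grafts:

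- Section 4b: "Bone morphogenic protein is effective in obtaining fusion but is used off label, has multiple side effects, and is expensive to hospital systems". It says that stem-cell products "avoids pain related to the graft donor site and have a far better safety profile than BMP".
- Section 3, Methods: "All anterior fusions will use BMP; the study only applies to the posterior fusion". Section 4c repeats this when it lists "type of bone graft used for the anterior procedure (all will be bone morphogenic protein combined with local autograft" as a data item.
- Section 6c, on consent: "Risk and benefits of surgery as well as specific risks related to bone graft products will be presented".

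Sections 3 and 4b set the design at five posterior grafts with 20 patients each.

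**The concern.** 7n looks incomplete against the application's own text. Placing a graft is part of a surgical process, 7i is ticked Yes, and 7n already reports one graft-specific risk, that of iliac harvest. One would expect the other four randomised grafts to be treated in the same way, above all BMP, which 4b describes as having multiple side effects. Item 7p, shortly after, asks whether benefits outweigh risks, so a one-sided list could tilt that judgement.

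Two further points seem to follow. The safety remark in 4b favours stem-cell products over BMP, yet no arm is free of BMP. And harvest pain and product safety help to motivate the study, while 4c names no complication and no iliac-site pain variable. If such data were never collected, the trial could say nothing about the harms it cites as its reason.

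**Working it through.** **Counts.** Inputs: five arms with 20 patients per arm (sections 3 and 4b).

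- Total: 5 × 20 = 100, which agrees with the enrolment figure in 6d.
- Iliac autograft, the only graft whose risk 7n describes: 20.
- Posterior BMP: 20. Donor-tissue products: 3 × 20 = 60. Posterior products with no risk described in 7n: 20 + 60 = 80.
- Anterior BMP: 100 of 100. Arms free of BMP: 0 of 5.

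The counts behind the concern are therefore right. What matters is what each one implies.

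**Anterior BMP, 100 of 100.** Section 7 asks what the research plan involves. Anterior BMP is not randomised, section 3 confines the study to the posterior fusion, and 4d counts the fusion surgery as standard care. Leaving a component common to all arms out of a research-risk item is defensible. The figure that bears on 7n is 80.

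**Posterior products, 80 of 100.** 7n is silent, but it does not say that these products are free of risk. The same committee reads in 4b that BMP is used off label and has side effects, and in 6c that product risks will be explained before surgery. This is an omission in one answer, not two statements that conflict. Privacy shows the same pattern: 7a is ticked Yes, 7n has no entry for it, and section 8 deals with it.

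**The safety remark in 4b.** Section 4a limits the objective to the posterior fusion. The text that follows the remark limits randomisation to the posterior part of the operation. 4c says that every anterior graft is BMP. A reader can already tell that the remark concerns the posterior graft.

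**The data list in 4c.** It is introduced as what data collection includes, and the form asks for data forms to be attached; none are in the reviewed text. The VAS and Oswestry scores are secondary endpoints in section 3, yet 4c does not list them either. A list that omits planned endpoints cannot show that complications go unrecorded.

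**What a safety table could add.** No section sets a safety comparison as an aim. If complications were tabulated and one arm had none, the exact two-sided 95% upper limit would be 1 − 0.025^(1/20) = 0.168, or 16.8%. Such a table could only be descriptive, and with anterior BMP in every arm, harms from BMP would not separate cleanly by posterior graft.

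**The case for a change.** The strongest case for a change rests on the 80 patients. The study itself assigns their posterior product, so neither the standard-care argument nor the No ticks for drugs and devices removes those products from 7n. Iliac harvest is reported under surgical processes, and the other grafts belong there just as much. The promise in 6c concerns what patients are told, whereas 7n is a separate written answer to the committee. The edit would cost almost nothing.

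This stands as a remark on completeness. A committee could fairly ask for 7n to be brought into line with 4b and 6c. It does not become a fault in the trial's design or analysis: the edit would write down risks that the application already acknowledges, and it would leave allocation, endpoints and the primary comparison as they are. The rest of the case does not stand. A sentence added to 4b would repeat what is there, and a new iliac-site pain score would be an extra endpoint, not the correction of an error.

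**Conclusion.** No change to the plan is called for. 7n describes a graft risk for 20 of 100 patients and none for the products randomised to the other 80. That is a documentation gap of low priority, with no effect on the estimate or test of posterior fusion, on the sample size, or on the VAS and Oswestry endpoints.

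This rests on three assumptions. First, anterior BMP belongs to the surgery that 4d calls standard care; 4d does not name BMP, but sections 3 and 4c make it common to all arms. Second, the consent discussion covers product risks as 6c promises; the consent form was not available, so this could not be checked. Third, 4c is not the full data list, as the absence of VAS and Oswestry from it indicates. If the third failed and complications were not recorded at all, the trial would be silent on harms, but its stated objective would be untouched.
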